# 17.5. Analysis of safety outcomes

The analysis of the following safety outcomes should follow the ITT principle.

**17.5.1. Safety Outcome 1: Failure to administer intervention due to AE** This outcome will assess if there is a difference in the occurrences of the failure to administer the intervention due to an AE. This is can occur in two possible ways:

- Failure to administer the intervention due to any adverse event during preparatory processes (tracheal toilet or BAL)
- Failure to complete administration of the intervention due to any adverse event during administration of the intervention (regardless of which arm of allocation)

Adverse events recorded from randomisation up to final trial intervention will be the period when this outcome could be observed.

# 17.5.1.1. Derivation

The details of failure to administer intervention can be found on the Treatment CRF.

A failure to administer the intervention due to any adverse event during preparatory processes (tracheal toilet or BAL) is indicated where the variable TRTINSTC=" Intervention not done" and the variable TRTISTRC = "F - Adverse Event during preparatory process".

A failure to complete administration of the intervention due to any adverse event during administration of the intervention is indicated where the variable TRTINSTC=" Intervention not completed" and TRTISTRC is one of ("E - Adverse Event", "G - Serious Adverse Event").

# Form prepared: 16/04/2024 v2.0 for BESS Page 23 of 30

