3.6.2 Secondary Outcomes/Endpoints

The secondary outcome measures for the trial (WP-A) are:

For efficacy:

- 1. duration of post-extubation non-invasive respiratory support (all forms of non-invasive ventilation: e.g. nasal CPAP and nasal high low oxygen)
- 2. duration of oxygen supplementation
- 3. number of trial interventions given (both poractant and placebo)
- 4. use of steroids to assist extubation
- 5. duration of stay on PICU and in hospital;
- 6. change over time from baseline of Ventilation Index (VI), Oxygenation Index (OI) and Oxygenation Saturation Index (OSI) while mechanically ventilated, & SpO₂/FiO₂ (SF) ratio.¹
- the score (value) of parent reported outcome measure of respiratory symptoms the "Liverpool Respiratory Symptom Questionnaire" (LRSQ) at 6m (+/-1m) and 12m (+/-1m) (20);

IRAS 220853 Page **20** of **87**

¹ VI and OI are validated physiological measurements reflecting respiratory function (gas exchange) normalised for level of respiratory support provided by MV, but require blood sampling(21). OSI is a validated physiological measurement reflecting respiratory function (gas exchange) normalised for level of respiratory support provided by MV that does not require blood sampling (41). The SF ratio is a non-invasive measure of respiratory function and can be calculated in situations where invasive blood gas monitoring and MV has ceased (22).

8. time from randomisation to meeting study criteria for readiness for Spontaneous Breathing Test

For safety:

- 1. failure to administer the intervention due to any adverse event during preparatory processes (tracheal toilet or BAL)
- 2. failure to complete administration of the intervention due to any adverse event during administration of the intervention (regardless of which arm of allocation)
- 3. incidents of 'air leak' (pneumothorax and pneumomediastinum) occurring before discharge from PICU
- 4. other adverse events and serious adverse events associated with the intervention
- 5. any need to replace the endotracheal tube
- 6. parent reported readmission to hospital (all causes) up to 90 days post randomisation
- 7. death during PICU admission
- 8. all-cause mortality at 90 days post randomisation

IRAS 220853 Page **21** of **87**

Table 1: Objectives and Outcome Measures

Objectives	Outcome Measures	Timepoint(s) of evaluation of this outcome measure (if applicable)

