10 SAFETY REPORTING

10.1 Terms and Definitions

"Adverse Event (AE)"

An adverse event (AE) is any untoward medical occurrence in a subject to whom a medicinal product has been administered, including occurrences which are not necessarily caused by or related to that product.

Therefore an AE is any unfavourable or unintended change in the function (symptoms), structure (signs) or chemistry (laboratory data) in a subject to whom an IMP has been administered, including occurrences which are not necessarily caused by or related to that product.

"Adverse Reaction (AR)"

An adverse reaction (AR) is any untoward and unintended response in a subject to an IMP that is related to any dose administered to that subject.

Therefore an AR is any unfavourable or unintended change in the function (symptoms), structure (signs) or chemistry (laboratory data) in a subject that is related to any dose of an IMP administered to that subject.

"Unexpected Adverse Reaction (UAR)"

An unexpected adverse reaction (UAR) is an adverse reaction the nature and severity of which is not consistent with the information about the medicinal product in question set out in the Investigator's Brochure (IB) or the SPC, which may be referenced where the IMP in question is a product with a marketing authorisation.

"Serious Adverse Event (SAE), "Serious Adverse Reaction, or Unexpected Serious Adverse Reaction"

A serious adverse event (SAE) is an AE, AR or UAR respectively that:

- results in death;
- is life threatening (places the subject, in the view of the Investigator, at immediate risk of death
 from the experience as it occurred this does not include an adverse experience that, had it
 occurred in a more severe form, might have caused death);
- requires hospitalisation or prolongation of existing hospitalisation (hospitalisation is defined as
 an in-patient admission, regardless of length of stay, even if the hospitalisation is a
 precautionary measure for continued observation hospitalisations for a pre-existing
 condition, including elective procedures that have not worsened, do not constitute an SAE);
- results in persistent or significant disability or incapacity (substantial disruption of one's ability to conduct normal life functions);
- consists of a congenital anomaly or birth defect (in offspring of subjects, or their partners, taking the IMP regardless of time of diagnosis);
- other important medical events (these may not result in death, be life-threatening, or require

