# 17.3. Compliance with treatment

Accountability logs and treatment CRFs will be assessed to determine treatment compliance. For each dose, the number of participants expected to receive the dose and the number and percentage actually receiving the full dose will be summarised by allocated treatment group and overall. Reasons for participants not receiving doses will be presented.

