#### 17.5.1.2. Analysis

The total number of occurrences of failure to administer intervention due to adverse event will be presented overall and for both treatment groups and also the number of patients in each group will be reported.

A two-way table of the frequency failed intervention delivery per infants by allocated treatment group will be presented. The comparative analysis between arms will be as described in section 17.4.3.2.

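### SAP 17.5.1.1 can miss a dose prevented by a serious adverse event during tracheal toilet or BAL if the site records reason G instead of F

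*SAP*

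**What the plan says.** SAP 17.5.1 states the preparatory component of Safety Outcome 1 as "Failure to administer the intervention due to any adverse event during preparatory processes (tracheal toilet or BAL"). Protocol 3.6.2 has the same definition: "failure to administer the intervention due to any adverse event during preparatory processes (tracheal toilet or BAL"). The second component is failure to complete because of an adverse event while the intervention is being given. Neither component is limited by seriousness, and Protocol 10.1 treats a serious event as a kind of adverse event: "A serious adverse event (SAE) is an AE, AR or UAR respectively that" meets one of the listed criteria.

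SAP 17.5.1.1 then turns the two components into rules on two Treatment CRF variables, the intervention status (TRTINSTC) and the reason (TRTISTRC):

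- Preparatory failure: "TRTINSTC=' Intervention not done' and the variable TRTISTRC = 'F - Adverse Event during preparatory process".
- Failure to complete: "TRTINSTC=' Intervention not completed' and TRTISTRC is one of ('E - Adverse Event', 'G - Serious Adverse Event").

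The output rests on these rules. SAP 17.5.1.2 says: "The total number of occurrences of failure to administer intervention due to adverse event will be presented overall and for both treatment groups". It adds the number of patients affected in each group, and compares the arms by the method of 17.4.3.2 (chi-squared test for trend, or Fisher's exact test when expected counts are small).

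**The concern.** The two rules are not built alike. For failure to complete, the SAP lists both an adverse-event code and a serious-event code. For preparatory failure it lists one code, F, and does not say what happens to a serious event in that phase.

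F and G also classify different things. F describes timing and G describes seriousness, yet both are values of the same reason variable. A serious event during lavage that stops the dose fits both labels. If the site enters one reason, its choice of label can decide whether the event reaches the safety outcome.

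At stake is whether a prespecified safety outcome about the trial procedure can leave out events that its own definition includes, and that are serious by construction.

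**Working it through.** The plan states no figure on this point, so there is nothing to reproduce. The check is to run the rule over every combination and compare the result with the definition.

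**Inputs.** Status (SAP 17.5.1.1): not done, not completed. Reason (same section): E, F, G. The SAP names only these three and does not give the full list.

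**Rule.** Component 1 = not done AND F. Component 2 = not completed AND (E or G). Counted = component 1 OR component 2. There are 2 × 3 = 6 combinations.

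| Status | Reason | Component 1 | Component 2 | Counted | In scope under the definition? |
|---|---|---|---|---|---|
| not done | E | no | no | no | only if the event fell in the preparatory phase |
| not done | F | yes | no | yes | yes |
| not done | G | no | no | no | only if the event fell in the preparatory phase |
| not completed | E | no | yes | yes | yes, if during administration |
| not completed | F | no | no | no | not as failure to complete, which needs an event during administration |
| not completed | G | no | yes | yes | yes, if during administration |

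Three of the six combinations are counted and three are not. Nothing in either document assigns the three uncounted ones to a component, and nothing says that a serious preparatory event must be coded F.

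**Would another output pick the event up?**

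- SAP 17.3: "Reasons for participants not receiving doses will be presented". SAP 14.2 likewise presents reasons for premature discontinuation. The missed dose would appear there, but not in Safety Outcome 1.
- SAP 20.1 limits the AE and SAE tables to participants who received at least one dose. An infant never dosed because of a serious event before the first procedure is outside that dataset. Safety Outcome 1 follows intention to treat (SAP 17.5) and is where that failure should be counted.
- SAP 21 has an independent statistician program the safety analysis from the same SAP. That would reproduce the omission and not reveal it.

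**Can the loss be sized?** The ceiling on procedures is 3 × 142 = 426 per arm (maximum of three doses, Protocol 2; 142 per group, Protocol 11.3). This limits procedures and does not estimate failures. The audit in Protocol 3.4.2, with 7 of 27 children desaturating, used five instillations of 1 mL/kg where the trial uses two. It describes transient events and does not call them serious. It shows that lavage can provoke events, but not how often a serious one would prevent a dose. Neither figure sizes the loss.

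**The case against.** The strongest reply is that F already does the job. Its label has no seriousness limit, a serious event is an adverse event under Protocol 10.1, and F is the only named code that identifies the preparatory phase. A careful site would choose F and the event would be counted. The Treatment CRF and its completion guidance are also not in the documents. The form may block G with not done, may allow several reasons, or may have codes that the SAP does not mention. All of this stands. It makes the loss conditional, but it does not make the rule complete, because the SAP neither tells sites to prefer F nor says what to do with a not-done record under G.

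A second reply concerns the other two uncounted combinations, and it also stands. A reader might infer that not done with E and not completed with F are lost in the same way. The documents do not support that. Not done with E may be a dose withheld for an event before preparation began, which is outside the definition. Not completed with F does not fit a component that requires an event during administration.

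A third reply is that the event does not vanish. Serious events must be reported to the trials centre within 24 hours (Protocol 10.8.3), and reasons for missed doses are presented. That is right, apart from the never-dosed infant, who is outside the AE and SAE tables. Finally, both arms have the same preparation (Protocol 8.1.1), so there is no evident reason for miscoding before the first dose to differ by arm.

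**Conclusion.** The mismatch between definition and derivation is real but narrow. A serious event during tracheal toilet or BAL that a site records as not done with reason G is in scope and meets neither component, so it can be missed. The conclusion assumes that the form permits that combination and that the site enters G without F.

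A reader might go further and infer that serious preparatory failures are in fact being dropped, or that the count is too low in either arm. The documents do not show this. Without the CRF the number of affected records cannot be estimated and may be zero. If failures are few, one or two such records could change the table in SAP 17.5.1.2, but that is a conditional statement. The primary outcome is untouched. The point merits a change because the outcome is prespecified, the events concerned are serious, and the correction is small.

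**What to change.** Amend SAP 17.5.1.1 before the randomisation codes are released to the statistical team (the milestone in SAP 15):

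1. Keep not done with reason F as a preparatory failure.
2. Review every not-done record with reason G or E, blind to arm. Count it as a preparatory failure if the event occurred during tracheal toilet or BAL. List doses withheld for an earlier event separately.
3. Send not completed with reason F to the same review. Do not count it automatically as failure to complete.

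The review should use the AE or SAE description and existing source notes. Protocol 10.8.3 says that the SAE form asks for date of onset and does not mention time, so the onset field alone may not separate lavage from the hours before it. Extracts should omit anything that reveals allocation.

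The cost is a few lines of SAP text, a small code change and blinded reading of what should be a handful of records. It needs no new assessments of participants, though sites may have to supply existing notes. Some records may remain unclassifiable and should be listed as such.

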#### 17.5.1.2. Analysis

The total number of occurrences of failure to administer intervention due to adverse event will be presented overall and for both treatment groups and also the number of patients in each group will be reported.

A two-way table of the frequency failed intervention delivery per infants by allocated treatment group will be presented. The comparative analysis between arms will be as described in section 17.4.3.2.

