## 9.2. Secondary outcomes

- Time from randomisation to meeting criteria for readiness for spontaneous breathing test (SBT)
- Number of trial interventions given
- Change from baseline of ventilation index, oxygenation index, and oxygenation saturation index whilst on MV
- Change from baseline of SpO2/FiO2 (SF) ratio
- Duration of oxygen supplementation
- Use of steroids to assist extubation
- Duration of post-extubation non-invasive respiratory support
- Duration of stay at Paediatric Intensive Care Unit (PICU) and in hospital
- Failure to administer intervention due to any adverse event (AE) during preparatory processes
- Failure to complete administration of intervention due to any AE during administration of intervention
- Incidence of pneumothorax or pneumomediastinum before discharge from PICU
- Any need to replace the endotracheal tube
- Parent-reported readmission to hospital
- Death during PICU admission
- All-cause mortality at 90 days post-randomisation
- Liverpool Respiratory Symptom Questionnaire (LRSQ) score

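### SAP 17.5.1 pools preparation failures and administration failures into one comparison, although the protocol and SAP 9.2 list them as two outcomes; this can dilute an excess caused by instilling surfactant

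*SAP*

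**What the plan says.** Protocol 3.6.2 numbers two safety outcomes. The first is a dose not given because of an adverse event during tracheal toilet or lavage. The second is "failure to complete administration of the intervention due to any adverse event during administration of the intervention". Protocol Table 1 gives each its own row.

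SAP 9.2 also has two bullets: "Failure to administer intervention due to any adverse event (AE) during preparatory processes" and "Failure to complete administration of intervention due to any AE during administration of intervention".

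SAP 17.5.1 then treats them as a single Safety Outcome 1: "This outcome will assess if there is a difference in the occurrences of the failure to administer the intervention due to an AE". It names the two kinds of failure as two ways in which that one outcome can arise. SAP 17.5.1.1 derives each kind from its own combination of TRTINSTC and TRTISTRC codes. SAP 17.5.1.2 does not carry the split forward: "The total number of occurrences of failure to administer intervention due to adverse event will be presented overall and for both treatment groups", and then "A two-way table of the frequency failed intervention delivery per infants by allocated treatment group will be presented". The comparison is referred to SAP 17.4.3.2, which is a chi-squared test for trend, or Fisher's exact test where expected cell counts are not above five. Safety Outcome 2 is air leak, so administration failure is not picked up as an outcome later in the section.

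**The concern.** The two kinds of failure carry different information about the drug. Under protocol 8.1.1, both arms have the same saline tracheal toilet and lavage before the intervention, and before the first dose this precedes any exposure. What then goes down the tube differs: surfactant in one arm, an equal volume of air in the other. Protocol 3.4.2 names bradycardia, hypotension, tube blockage and desaturation as reactions associated with giving poractant alfa. An administration stopped by an adverse event is therefore the more drug-specific of the two outcomes, while preparation failure is largely background shared by the arms.

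Adding a shared background to both arms leaves the absolute difference almost unchanged but raises the variance, so a test on the pooled outcome is less likely to detect an excess confined to administration. A reader of the final report would also find no between-arm result for either outcome as listed.

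**Working it through.** **1. Sample size per arm.** The plan gives no rate or power for these outcomes; its only relevant figure is the number per arm. Protocol 11.3 uses coefficients of variation 2.5/4.83 = 0.518 and 2.5/4.08 = 0.613, and ratio 4.08/4.83 = 0.845. The log-scale variances are ln(1 + 0.518²) = 0.237 and ln(1 + 0.613²) = 0.319. The log-scale difference is ln(0.845) − ½(0.319 − 0.237) = −0.209. Then n = (z₁₋α/₂ + z₁₋β)² × (0.237 + 0.319)/0.209², which with unrounded inputs gives 99.5, so 100 (80% power), and 133.2, so 134 (90% power). Dropout: 134/0.95 = 141.05, so 142 per arm. The stated figures reproduce.

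**2. Assumed rates (none are in the documents).** Administration failure, given that it is attempted: a = 8% under surfactant and 1% under placebo. Preparation failure: q, equal in both arms. Each infant is scored yes/no, and a preparation failure means that administration is not attempted.

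**3. Formulas, per randomised infant.** Pooled risk = q + (1 − q)a. Risk of administration failure = (1 − q)a. For q = 5%: surfactant 0.05 + 0.95 × 0.08 = 12.6%; placebo 0.05 + 0.95 × 0.01 = 5.95%. The difference is 6.65 points, against 7 points with no preparation failures, but the base risk is much higher.

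**4. Exact binomial power.** 142 per arm, two-sided 0.05, chi-squared if expected counts exceed five and Fisher otherwise (the SAP 17.4.3.2 rule applied to a 2×2 table), counting only rejections that show an excess under surfactant:

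| q | Pooled risk, surfactant v placebo | Power, pooled test |
|---|---|---|
| 0% (administration failure alone) | 8.0% v 1.0% | 0.84 |
| 1% | 8.9% v 2.0% | 0.76 |
| 3% | 10.8% v 4.0% | 0.60 |
| 5% | 12.6% v 6.0% | 0.49 |
| 10% | 17.2% v 10.9% | 0.33 |

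Testing administration failure separately, with preparation failures still removing some infants from risk, keeps power of 0.84 at q = 1%, 0.81 at 5% and 0.78 at 10%.

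**5. Other assumed rates.** For 6% v 1%, power is 0.59 alone and 0.52, 0.38, 0.30 and 0.20 pooled at q = 1%, 3%, 5% and 10%. For 10% v 2%, it is 0.85 alone and 0.77, 0.64, 0.55 and 0.39 pooled.

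**6. Worked counts.** Administration failures of 9 v 1 have expected count 5, so Fisher applies: p = 0.019. Adding 7 preparation failures to each arm gives 16 v 8 and chi-squared p = 0.088. Adding 1 to each arm gives 10 v 2 and chi-squared p = 0.018, so here the conclusion does not change.

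**7. Limit of the calculation.** SAP 17.5.1.2 tabulates the number of failures per infant. If counts from 0 to 3 are kept, the trend test or Fisher's test on a larger, sparse table applies. That case was not modelled.

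**The case against.** - **Masking is not shown.** A reader might infer that lavage failures will hide a surfactant harm. The documents do not support that, because they give no failure rates. The outcome needs an adverse event that stops the dose, not merely a desaturation. Protocol 3.4.2 describes the small-volume lavage as safe and well tolerated. Its only figures, 7 of 27 children with transient desaturation, come from a larger-volume procedure, and it mentions no abandoned procedures. At q = 0.5%, pooled power is still 0.80 against 0.84. This stands: pooling can dilute, and how much is unknown.
- **No planned estimate is biased.** It is tempting to say that the reported relative risk would be pulled towards 1. SAP 17.4.3.2 yields a test statistic and a p-value, and no relative risk is planned for this outcome. This stands.
- **The split may be visible elsewhere.** SAP 17.3 summarises full doses received by arm and presents reasons for doses not received. SAP 17.4.3.2 compares the number of completed interventions, and SAP 20.2 tabulates adverse events. These mitigate only in part: SAP 17.3 does not say that the reasons will be shown by arm, and none of the three compares the arms by type of failure.
- **Preparation failure is not purely background.** Preparation before the second and third doses follows exposure, and protocol 7.4 expects surfactant to track back up the tube. Those failures could differ by arm. This limits the equal-rates assumption, and it is a further reason to report the two types apart.
- **Events may be too few to test.** That may be so, but a pooled total is then still less informative than two counts by arm.

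**Conclusion.** The inconsistency is firm. It lies within the SAP, between 9.2 and 17.5.1, so it does not depend on which protocol version the SAP follows. As written, the plan gives no between-arm comparison for either listed outcome, and no reason is given for merging them.

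The consequence is conditional. Under the assumed 8% v 1%, equal preparation failure in both arms and yes/no scoring, pooling costs about 8 points of power if preparation failure is 1% (0.84 to 0.76) and about 35 points if it is 5% (0.84 to 0.49). The direction follows from the arithmetic whenever preparation failures are shared by the arms; the size rests wholly on assumed rates. The point should be corrected in the SAP, but it is not evidence that a harm would be missed.

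**What to change.** In SAP 17.5.1.2, give each of the two outcomes its own count of events and infants, its own two-way table and its own between-arm comparison, using the TRTINSTC and TRTISTRC codes already set out in 17.5.1.1. The main analysis of each should be per randomised infant by allocated arm, because SAP 17.5 requires the ITT principle for these outcomes.

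Add a supplementary summary of administration failures among attempted instillations. This allows for doses at which a preparation failure left nothing to observe. It conditions on a post-randomisation event, so it should not be the main analysis. Keep the pooled total as description only.

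The cost is SAP wording and one more table. No new data are needed, and SAP 12 plans no multiplicity adjustment, so separating the outcomes spends no alpha.
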